9.3.3. Adverse Event Intensity Grading

All clinical AEs encountered during the clinical study will be reported on the AE page of the eCRF. Intensity of AEs will be graded based on a modified CTCAE, Version 5.0 and reported in detail as indicated on the eCRF. For any AEs not found in the CTCAE, a description of intensity grading can be found in [Appendix 12](#) and below:

- | | |
|----------|---|
| Grade 1: | Mild; asymptomatic or mild symptoms; clinical or diagnostic observations only; intervention not indicated. |
| Grade 2: | Moderate; minimal, local, or noninvasive intervention indicated; limiting age-appropriate instrumental activities of daily living. |
| Grade 3: | Severe or medically significant but not immediately life-threatening; hospitalization or prolongation of hospitalization indicated; disabling; limiting self-care activities of daily living. |
| Grade 4: | Life-threatening consequences; urgent intervention indicated: by definition also a SAE. |

Death will not be recorded as a Grade 5 severity - rather the underlying condition will be recorded, and its severity graded, with death regarded as an outcome.

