9.3.2. Adverse Events

An AE is any untoward medical occurrence in a participant or clinical investigation participant administered a pharmaceutical product and which does not necessarily have to have a causal relationship with the intervention. An AE can therefore be any unfavorable and unintended sign (including an abnormal laboratory finding, for example), symptom, or disease temporally associated with the use of an IMP, whether or not considered related to the product. All AEs encountered during the clinical study will be reported in detail in the source documents and documented in the eCRF, from the date of participant consent throughout the follow-up visit. Pre-existing conditions that worsen during a study are to be reported as AEs, with the exception of expected variation in ITP disease activity itself.

Unexpected progression, signs, or symptoms of the disease under study (ITP) are not AEs and are not to be recorded on the AE page of the eCRF unless the event meets the definition of an SAE or is not consistent with the typical clinical course of the participant's disease as established by the participant's medical history. Worsening of the disease under study or other disease-related symptoms should be recorded as an AE only if the event meets the definition of an SAE or is not consistent with the typical clinical course of the disease.

Definitions:

The below guidelines should be followed when recording AEs:

- Medical terms: Whenever possible, use recognized medical terms when recording AEs on the AE eCRF. Do not use colloquialisms or abbreviations.
- Diagnosis: If known or suspected, record the diagnosis (except for eg, hypoglycemia) rather than component signs and symptoms on the AE eCRF and SAE form (eg, record congestive heart failure rather than dyspnea, rales, and cyanosis.) However, signs and symptoms that are considered unrelated to an encountered syndrome or disease should be recorded as individual AEs on the AE eCRF and SAE form.
- Death: Death is an outcome of an event. The event that resulted in the death should be recorded and reported on the AE eCRF and SAE form (except for sudden, unexplained death).

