9.3.9.6. Adverse events of special interest

An AESI is an AE (serious or nonserious) of scientific and medical concern specific to the Sponsor's product or program, for which ongoing monitoring and immediate notification (within 24 hours) by the Investigator to the Sponsor is required. Such events may require further investigation in order to characterize and understand them. Adverse events of special interest may be added, modified, or removed during a study by protocol amendment; they include:

- Pregnancy of a female participant entered in a study and received at least one dose of the IMP as well as pregnancy occurring in a female partner of a male participant entered in a study with IMP;
 - Pregnancy occurring in a female participant entered in the clinical trial or in a female partner of a male participant entered in the clinical trial will be qualified as an SAE only if it fulfills one of the seriousness criteria (see [Appendix 12](#)).
 - In the event of pregnancy in a female participant, IMP must be discontinued.
 - Follow-up of the pregnancy in a female participant or in a female partner of a male participant is mandatory until the outcome has been determined (See [Appendix 13](#)).
- Symptomatic overdose (serious or nonserious) with IMP

- Increase in ALT $>3 \times$ ULN (See [Appendix 15](#) for follow-up instructions). If such laboratory values have been determined, follow-up within 72 hours of the same value and total bilirubin levels is required and if value is repeated (eg, ALT $>3 \times$ ULN), such value shall be reported as well together with the repeated total bilirubin values and any other laboratory values to determine the cause of the initially determined ALT increase.
- Any Grade 4 or 5 infection where the participant is hospitalized ≥ 24 hours and/or requires emergency care and/or requires intravenous antibiotics.
- Any occurrence of uveitis (including Vogt-Koyanagi-Harada disease [VKHD])

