Appendix 12.3 Recording and follow-up of AE and/or SAE

AE and SAE recording

- When an AE/SAE occurs, it is the responsibility of the Investigator to review all documentation (eg, hospital progress notes, laboratory reports, and diagnostics reports) related to the event.
- The Investigator will then record all relevant AE/SAE information.
- It is **not** acceptable for the Investigator to send photocopies of the participant's medical records to the Sponsor's representative in lieu of completion of the required form.
- There may be instances when copies of medical records for certain cases are requested by the Sponsor's representative. In this case, all participant identifiers, with the exception of the participant number, will be redacted on the copies of the medical records before submission to the Sponsor's representative.
- The Investigator will attempt to establish a diagnosis of the event based on signs, symptoms, and/or other clinical information. Whenever possible, the diagnosis (not the individual signs/symptoms) will be documented as the AE/SAE.

Assessment of intensity

The NCI-CTCAE Version 5.0 will be used to assess the severity of AEs/SAEs.

The Investigator will make an assessment of intensity for each AE and SAE reported during the study and assign it to 1 of the following categories:

- | | |
|----------|---|
| Grade 1: | Mild; asymptomatic or mild symptoms; clinical or diagnostic observations only; intervention not indicated. |
| Grade 2: | Moderate; minimal, local, or noninvasive intervention indicated; limiting age-appropriate instrumental activities of daily living. |
| Grade 3: | Severe or medically significant but not immediately life-threatening; hospitalization or prolongation of hospitalization indicated; disabling; limiting self-care activities of daily living. |
| Grade 4: | Life-threatening consequences; urgent intervention indicated: by definition also a SAE. |

Death will not be recorded as a Grade 5 severity - rather the underlying condition will be recorded, and its severity graded, with death regarded as an outcome.

An event is defined as “serious” when it meets at least 1 of the predefined outcomes as described in the definition of an SAE, NOT when it is rated as severe.

Assessment of causality

- The Investigator is obligated to assess the relationship between study intervention and each occurrence of each AE/SAE.

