**Table 8 - Selections for AESIs and other AEs of interest**

AESIs and other AEs of interest	Selection
Pregnancy	e-CRF “Adverse Events”, AE category=“Pregnancy”, AESI checked yes
Symptomatic overdose (serious or nonserious) with IMP	e-CRF “Adverse Events”, AE category=“Overdose”, AESI checked yes (complementary e-CRF “Overdose”, “Overdose of Rilzabrutinib” checked yes, “Symptomatic Overdose” checked yes)
Increase in alanine transaminase (ALT) >3 × ULN	e-CRF “Adverse Events”, AE category=“ALT increase”, AESI checked yes (Complementary e-CRFs “ALT Increase – Associated Signs and Symptoms” and “ALT Increase – Trigger Factors”)
Infection: Grade 4 or 5 infection where the participant is hospitalized ≥24 h and/or requires emergency care and/or requires IV antibiotics.	e-CRF “Adverse Events”, AE category=“Infection”, AESI checked yes (complementary e-CRF “Infection event form”)
Infection	SOC “Infections and Infestations”

AESIs and other AEs of interest	Selection
Bleeding event	SMQ = Haemorrhages, #20000038, broad and narrow search
Neutropenia	CMQ10801 based on the list of PTs in Section 5.8 a
Anemia	SMQ = Haematopoietic erythropenia, #20000029, broad and narrow search
Thromboembolic events	SMQ = Embolic and thrombotic events, #20000081, broad and narrow search
Gastrointestinal events	HLT "Diarrhoea (excl infective)", "Nausea and vomiting symptoms"

a The list of terms may be adjusted according to MedDRA version changes.  
eCRF = electronic case report form. SMQ = Standardized MedDRA queries. CMQ = customized MedDRA queries. HLT = high level term.

For treatment emergent infection ( $\geq$  Grade 2), bleeding ( $\geq$  Grade 2), and gastrointestinal events, the following analyses will be presented, in addition to those specified in [Table 7](#).

- n (%) of participants with any TEAE, treatment emergent SAE, TEAE leading to death, TEAE leading to permanent study intervention discontinuation, TEAE related to IMP.

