#### **Analysis of gastrointestinal events for each PT (ie, nausea, vomiting and diarrhoea, respectively)**

- Maximal CTCAE grade: Grades 1 to 5
- Worst outcome (from most to least severe): Fatal, Not Recovered/Not Resolved, Recovering/Resolving, Recovered/Resolved with sequelae, Recovered/Resolved, Unknown
- Time to first onset in days: mean (SD), median, min, max
- Incidence rate
  - Frequency of events (ie, incidence) by interval of onset:  $\leq 1$  week,  $>1$  to 2 weeks,  $>2$  to 4 weeks,  $>4$  to 8 weeks,  $>8$  to 12 weeks,  $>12$  to 16 weeks,  $>16$  to 20 weeks,  $>20$  to 24 weeks, and  $>24$  weeks. The numerator is the number of participants with an occurrence of the event in the given interval. The denominator is the number of participants exposed at the beginning of the interval. Multiple occurrences of the same event for a participants can be counted in several intervals, but only once in the same interval.
  - Kaplan-Meier estimate of cumulative incidence rate at the end of Weeks 1, 2, 4, 8, 12, 16, 20, 24.
- Average duration of TEAEs
  - Average duration of TEAEs in days (ie, average duration across all resolved occurrences): mean (SD), median, min, max
  - Average duration by interval: 0 to 2 days,  $>2$  to 7 days,  $>7$  days to 1 month,  $>1$  month to 4 months,  $>4$  months

- Cumulative duration of TEAEs
  - Cumulative duration of TEAEs in days (total duration of events over time): mean (SD), median, min, max
  - Cumulative duration by interval: 0 to 2 days, >2 to 7 days, >7 days to 1 month, >1 month to 4 months, >4 months

Kalan-Meier curves will be provided for the time to each GI event (ie, nausea, vomiting and diarrhoea, respectively), as well as for the time to IMP discontinuation due to any GI events. Participants without any event will be censored at the end of the treatment-emergent period.

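### The protocol bars recording death as Grade 5, but the SAP tabulates Grade 5 events and the infection AESI refers to Grade 4 or 5

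*Protocol*

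**What the plan says.** **The recording rule.** Protocol 9.3.3 states "Intensity of AEs will be graded based on a modified CTCAE, Version 5.0", lists Grades 1 to 4, and closes with "Death will not be recorded as a Grade 5 severity - rather the underlying condition will be recorded, and its severity graded". Appendix 12.3 has the investigator make "an assessment of intensity for each AE and SAE reported during the study and assign it to 1 of the following categories". The categories are again Grades 1 to 4, followed by the same rule: "Death will not be recorded as a Grade 5 severity". Protocol 9.3.2 agrees: "Death is an outcome of an event".

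**Where Grade 5 is used all the same.**
- Protocol 9.3.9.6, infection AESI: "Any Grade 4 or 5 infection where the participant is hospitalized" for at least 24 hours, or needs emergency care or intravenous antibiotics.
- SAP Table 8: "Infection: Grade 4 or 5 infection where the participant is hospitalized", with the same care criteria. Events are selected from the AE form by the infection category and a ticked AESI box.
- SAP 3.6.2, TEAE overview: a row for Grade 5 TEAEs directly after the row for TEAEs leading to death.
- SAP 3.6.2, gastrointestinal events: "Maximal CTCAE grade: Grades 1 to 5".

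**Related text.** SAP 3.6.2 names NCI-CTCAE version 5.0 as the scale for all AEs and does not mention the protocol's modification. No SAP section maps a fatal outcome to Grade 5. Protocol 2.7.1, Table 4 describes the infection AESI more broadly, as covering infections that are either severe or serious.

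**The concern.** The SAP plans to count a grade that the protocol tells sites not to assign. An overview table could show no Grade 5 events beside a non-zero count of fatal TEAEs, with nothing to tell the reader that the zero comes from the recording rule.

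The same conflict reaches the infection AESI. Protocol 2.7.1 lists serious infection as one of three important potential risks. The words Grade 4 or 5 suggest that fatal infections were meant to be inside the AESI, but under the recording rule only Grade 4 can trigger it.

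**Working it through.** No figure in the plan is at issue and no arithmetic beyond set logic applies, so the check sets the passages side by side.

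1. **Grades a site may record.** Section 9.3.3 introduces its four-grade list for events not found in CTCAE, which could be read as limiting it to those. Its sentence on death carries no such limit, and Appendix 12.3 applies the four categories to each AE and SAE. Read together, the permitted set is {1, 2, 3, 4}.

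2. **Grade 5 row and gastrointestinal category.** {1, 2, 3, 4} ∩ {5} = ∅. If d participants have a fatal TEAE, the overview prints d in the row for TEAEs leading to death and 0 in the Grade 5 row, for every d. The gastrointestinal Grade 5 category is empty for the same reason.

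3. **If practice varies by site.** Suppose k of the d participants with a fatal TEAE are at sites that enter Grade 5 under unmodified CTCAE. The row then prints k, anywhere from 0 to d, and k reflects site convention rather than the number of deaths.

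4. **Infection AESI.** {1, 2, 3, 4} ∩ {4, 5} = {4}. The classification of a fatal infection is then:

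| Recorded grade of the fatal infection | Protocol 9.3.9.6 and SAP Table 8 | Protocol Table 4 |
|---|---|---|
| 4, care criterion met | AESI | AESI |
| 3 or lower | Definition not met; counted only if the site ticks the box anyway | AESI, since an event resulting in death is serious (Appendix 12.2) |

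5. **Where fatal events are still counted.** SAP 3.6.2 has the overview row for TEAEs leading to death. Table 7 tabulates those events by SOC and PT for adults in the 24-week double-blind period and cumulatively across periods. Deaths are summarized by primary cause and treatment period. Infections of Grade 2 or higher have their own count of TEAEs leading to death. Protocol 9.3.9.1 sets the same 24-hour limit for SAEs and AESIs.

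**The case against.** The best reply is that this is a wording conflict with little effect.

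- **Several instructions allow Grade 5.** Appendix 12.3 opens by naming NCI-CTCAE version 5.0, the SAP names it without modification, and 9.3.9.6 itself speaks of Grade 5. The eCRF is not among the documents, so whether it accepts Grade 5 is unknown. This stands: a reader might infer that the row must be zero, but that holds only where sites follow the protocol rule. The alternative, a count mixing two conventions, is no easier to interpret.
- **A fatal infection would ordinarily be graded 4.** The protocol defines Grade 3 as not immediately life-threatening and Grade 4 as life-threatening, and SAP 3.6.2 uses the worst grade. This narrows the AESI gap but does not close it, because the rule grades the underlying condition and not the outcome.
- **Table 8 does not filter on grade.** It relies on the tick, so a ticked fatal infection counts at any grade. This stands. The gap therefore needs both a grade of 3 or lower and an unticked box.
- **The row may not be printed.** Footnote a of Table 7 gives overview categories that include AEs leading to death and no Grade 5. That adds a second inconsistency within SAP 3.6.2.
- **Nothing inferential depends on it.** SAP 3.6 makes the safety analyses essentially descriptive, without testing. This stands and limits the weight of the point.

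**Conclusion.** The contradiction is real and should be resolved. Followed as written, the Grade 5 row and the gastrointestinal Grade 5 category are structural zeros; with mixed site practice they are uninterpretable. The infection AESI works as Grade 4, and the protocol gives two different descriptions of it. The size of any AESI undercount cannot be computed, because it depends on how many fatal infections are graded 3 or lower and left unticked. With few such events, one could change the AESI count.

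Two stronger readings go beyond the documents. A reader might infer that deaths or fatal infections drop out of the safety report; the fatal-TEAE, death and infection-specific summaries count them, and SAE reporting is unaffected. A reader might also infer that the general maximal-grade table understates fatal events; Table 7 states no grade range for it, and the protocol deliberately keeps severity and outcome apart. The efficacy analyses are untouched.

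**What to change.** **In SAP 3.6.2, choose one convention.**
- Derive an analysis Grade 5 for any TEAE whose recorded outcome is fatal, use it in the overview, maximal-grade and gastrointestinal tables, and keep the investigator's grade as a separate variable; or
- Delete the Grade 5 row and category and rely on the row for TEAEs leading to death.

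In either case, state the protocol's modification of CTCAE where the SAP names the scale, and align footnote a of Table 7 with the overview list.

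The cost is a SAP revision and, for the first option, one derivation. No new data are needed: the SAP already tabulates a fatal category under worst outcome for gastrointestinal events.

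**For the infection AESI, reconcile the passages.** Protocol 2.7.1 Table 4, 9.3.3, 9.3.9.6 and Appendix 12.3, together with the SAP 3.6.2 grading statement and Table 8, should make clear how an infection with fatal outcome is classified. Which definition applies is for the sponsor to settle. Protocol 9.3.9.6 provides for AESI changes by protocol amendment, and 12.1 requires IRB/IEC approval, so this part costs more than the SAP edit.

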9.3.4. Adverse Event Relationship to Study Medication

Investigators should use their knowledge of the study participant, the circumstances surrounding the event, and an evaluation of any potential alternative causes to determine whether or not an AE is considered to be related to any study drug (eg, rilzabrutinib or placebo), indicating "yes" or "no" accordingly.

The following guidance should be taken into consideration:

- Temporal relationship of event onset to the initiation of rilzabrutinib or placebo
- Course of the event, considering especially the effects of dose reduction, discontinuation of study medication, or reintroduction of rilzabrutinib or placebo (if applicable)
- Known association of the event with rilzabrutinib or placebo or with similar treatments
- Known association of the event with the disease under study
- Presence of risk factors in the study participant or use of concomitant medications known to increase the occurrence of the event
- Presence of non-treatment-related factors that are known to be associated with the occurrence of the event

9.3.5. Adverse Event Relationship to Standard of Care Medication

Investigators should use their knowledge of the study participant, the circumstances surrounding the event, and an evaluation of any potential alternative causes to determine whether or not an AE is considered to be related to their standard of care medication (eg, CSs or TPO-RA), indicating "yes" or "no" accordingly. For this study standard of care medications may only be reduced due to a safety concern (eg, a corresponding AE).

9.3.6. Treatment Unblinding to Determine Clinical Course

If deemed by the Investigator to be medically necessary in the event that a SUSAR occurs, to determine appropriate clinical treatment, the Investigator can unblind an individual participant via the IWRS after consultation with Sponsor medical monitor. See [Appendix 10](#) for UK country-specific requirements.

Instructions for Investigators to unblind are located in the Investigator Site File.

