6.4.4. Treatment Blinding/Unblinding

Allocation of participants to treatment groups will proceed through the use of an interactive web response system (IRT/IWRS) that is accessible 24 hours a day, 365 days a year.

- The randomized intervention kit number list is generated centrally by the IRT/IWRS.
- The randomization and intervention allocation are performed centrally by the IRT/IWRS. The IRT/IWRS generates the participant randomization list and allocates the intervention number and the corresponding intervention kits to the participants according to it.
- A randomized participant is a participant from the screened population who has been allocated to a randomized intervention by the IRT/IWRS regardless of whether the intervention was received or not.

The pharmacist or designee will be required to enter or select information that will include, but not be limited to; the user ID, and password, participant number, participant year of birth, as well as other information (as allowed locally). The pharmacist or designee will then be provided with a participant randomization number and treatment assignment. Once participant numbers and randomization numbers have been assigned, they cannot be reassigned. The randomization system will also send confirmation of the randomization, by email or fax, to the user. Specific instructions will be provided in the IWRS study reference guide. Access to the randomization code will be limited; all Sponsor personnel (and representatives), and site personnel who are directly involved in the conduct of the study will be blinded to randomization codes.

The treatment each participant receives will not be disclosed to the Investigator, study center personnel, participants, or the Sponsor or representatives on the clinical study team. Further details for blinding and dispensing of blinded treatment are provided in the Pharmacy Manual.

If deemed by the Investigator to be medically necessary, the Investigator can unblind a participant via the IWRS after consultation with Sponsor medical monitor (See [Appendix 10](#) for UK country-specific requirements).

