Sponsor PV operations/responsible third party may unblind the intervention assignment for any participant with a suspected unexpected serious adverse reaction (SUSAR). If the SUSAR requires that an expedited regulatory report be sent to one or more regulatory agencies, a copy of the report, identifying the participant's intervention assignment, may be sent to Investigators in accordance with local regulations and/or Sponsor policy.

At the facilities where the systemic drug concentration measurements and selected biomarkers are determined, the samples will be analyzed prior to data base lock leading to unblinding of responsible bioanalysts. Bioanalysts are excluded from the clinical trial team. One programmer may be unblinded to prepare the dataset for population PK analysis, and there will be strict procedures to maintain blind beyond the programmer.

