9.3.9.4. Regulatory reporting requirements for SAEs

- Prompt notification by the Investigator to the Sponsor of an SAE is essential so that legal obligations and ethical responsibilities towards the safety of participants and the safety of a study intervention under clinical investigation are met.
- The Sponsor has a legal responsibility to notify both the local regulatory authority and other regulatory agencies about the safety of a study intervention under clinical investigation. The Sponsor will comply with country-specific regulatory requirements relating to safety reporting to the regulatory authority, IRB/IEC, and Investigators.
- Serious adverse events that are considered expected will be specified in the reference safety information in the Investigator's Brochure.
- Investigator safety reports must be prepared for SUSARs according to local regulatory requirements and Sponsor policy and forwarded to Investigators as necessary.
- An Investigator who receives an Investigator safety report describing an SAE, SUSAR or any other specific safety information (eg, summary or listing of SAEs) from the Sponsor will review and then file it along with the Investigator's Brochure and will notify the IRB/IEC, if appropriate according to local requirements. It is the responsibility of the Sponsor to assess whether an event meets the criteria for a SUSAR, and therefore, is expedited to regulatory authorities.
- For the European Union, safety reporting to the agency is described in [Appendix 10.7](#).

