Appendix 10 Country-Specific Requirements

Appendix 10.1 UK country-specific requirements

- Synopsis and Section 5.2, Exclusion criteria, criterion 17: For participants in the UK, a positive QuantiFERON®-TB Gold Plus at Screening will result in exclusion. The 3 conditions to allow inclusion with a positive test do not apply to participants in the UK.
- Section 6.4.4, Treatment blinding/unblinding: For participants in the UK, the Investigator can unblind a participant via the IWRS if deemed medically necessary without previous consultation with the Sponsor medical monitor, but the Sponsor medical monitor should be notified.

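### Protocol Sections 6.4.4 and 9.3.6 set conflicting conditions for investigator unblinding, and outside the UK both put sponsor consultation first with no fallback

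*Protocol*

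**What the plan says.** Four places in the protocol bear on who may break the blind and when.

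- Section 6.4.4, the main blinding section: "If deemed by the Investigator to be medically necessary, the Investigator can unblind a participant via the IWRS after consultation with Sponsor medical monitor". The only condition is the investigator's view of medical need. The same section says the IWRS is available at all hours, every day of the year. It also gives sponsor pharmacovigilance, or a responsible third party, a separate power to unblind for SUSARs.
- Section 9.3.6, on unblinding to determine clinical course, opens: "If deemed by the Investigator to be medically necessary in the event that a SUSAR occurs, to determine appropriate clinical treatment". It continues: "the Investigator can unblind an individual participant via the IWRS after consultation with Sponsor medical monitor". It points to Appendix 10 for the UK and to the Investigator Site File for instructions.
- Section 9.3.9.4, on regulatory reporting: "It is the responsibility of the Sponsor to assess whether an event meets the criteria for a SUSAR".
- Appendix 10.1, for UK participants, allows the investigator to unblind "if deemed medically necessary without previous consultation with the Sponsor medical monitor, but the Sponsor medical monitor should be notified". This entry is written against Section 6.4.4 and does not name Section 9.3.6.

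**The concern.** The code break exists so that the treating physician can act on the assigned treatment when care depends on it. Section 9.3.6 sits in the safety chapter under a title that describes exactly that situation, so a site handling an acute event may well turn to it first. There it finds a condition that Section 6.4.4 does not contain, expressed in a regulatory reporting term whose assessment belongs to the sponsor. A site could wait for that assessment, or conclude that its case does not qualify.

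The consultation step is a separate matter. Outside the UK the system can release the code at any hour, but the investigator must first speak to the sponsor's medical monitor. The protocol does not say how long to wait or what to do if the monitor cannot be reached.

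**Working it through.** No arithmetic underlies the main point. The check is to set the rules side by side and apply them to the same cases.

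| Place | Condition | Sponsor step | Applies to |
|---|---|---|---|
| 6.4.4 | Medically necessary | Consultation before | All except the UK |
| 9.3.6 | Medically necessary and a SUSAR has occurred | Consultation before | All; UK sites sent to Appendix 10 |
| Appendix 10.1 | Medically necessary | Notification only | UK |

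**Case 1: a serious emergency outside the UK that is judged unrelated to study drug, or is already an expected reaction.** By the meaning of the abbreviation, a SUSAR must be suspected, unexpected and serious, so this event is not one. A serious bleed attributed to ITP is an example. An overdose (Section 6.5) is not in itself a SUSAR either. Section 6.4.4 allows the code break after consultation. The condition in 9.3.6 is not met.

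**Case 2: an event outside the UK that may be a SUSAR but has not been assessed.** Section 6.4.4 allows the code break after consultation. Under 9.3.6 the answer depends on whether the investigator may treat the event as a SUSAR or must await the sponsor's assessment under 9.3.9.4. The text does not say.

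**Case 3: an event outside the UK already assessed as a SUSAR.** The two sections agree.

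**Case 4: any medically necessary case in the UK.** Appendix 10.1 allows the code break, with notification. Section 9.3.6 sends UK sites to Appendix 10, where there is no SUSAR condition. The only loose end is that the appendix entry names 6.4.4 alone.

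The two sections therefore part in cases 1 and 2. Those are the cases in which a physician may need the assignment before any regulatory classification exists, or when none will follow.

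**Reach of the consultation rule.** The geographic regions in SAP Section 3.2.4 list 6 (Asia/Pacific) + 8 (West Europe) + 6 (East Europe) + 2 (North America) + 4 (South America) = 26 countries. Leaving out the UK, 26 − 1 = 25 are under prior consultation. UK enrolment is not given, so this cannot be turned into a number of participants.

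**The case against.** The strongest reply is that the protocol as a whole does not restrict code breaks to SUSARs. Section 9.3.6 does not contain the word only, and Section 6.4.4, whose heading names unblinding, gives a route for every medically necessary case. This is right. A reader of 9.3.6 alone might infer that the blind can be broken only after a SUSAR, and 6.4.4 contradicts that. What remains is that two sections state the same right differently, with no rule on which prevails.

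Second, the sponsor's SUSAR assessment in 9.3.9.4 is tied to expedited reporting to authorities. Investigators judge causality themselves (Section 9.3.4 and Appendix 12.3), and nothing says that they must await a sponsor classification before acting. This also stands. Waiting is a possible reading of 9.3.6, not a stated step. It does not help in case 1, where the event is not a SUSAR on anyone's assessment.

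Third, both sections ask for consultation, not approval. A reader might infer that the sponsor can block a code break, but no passage gives the medical monitor a veto. Delay is supported; blocking is not.

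Fourth, the UK difference has a stated origin: the amendment history records it as a country-specific requirement. That is brief, but it is a reason.

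Finally, the Investigator Site File, the IWRS study reference guide and the Pharmacy Manual are not available here, and contact pages were removed. They may describe a round-the-clock contact or an override. That makes the practical risk uncertain, but a site document should not have to settle a conflict within the protocol.

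**Conclusion.** The concern holds as an internal contradiction with a possible delay attached. Section 9.3.6 adds a SUSAR condition that Section 6.4.4 lacks, and a site relying on 9.3.6 alone could delay or forgo a permitted code break. Separately, outside the UK (25 of the 26 countries listed in the SAP) both sections require prior consultation and state no time limit or fallback.

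Three further readings go beyond the documents:

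- The SUSAR limit does not persist in the UK. Appendix 10.1 carries none, and 9.3.6 refers UK sites there.
- The planned total of about 224 participants (SAP Section 1.1) is not the number affected by prior consultation, because it includes any UK participants.
- It cannot be assumed that each code break is logged. No passage describes such a log.

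The conclusion rests on the protocol text alone. It assumes that sites may use 9.3.6 as their working rule in an emergency, and that the site-level instructions, which were not seen, do not override it. The size, power and error rate of the trial are not in question.

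**What to change.** 1. Delete the SUSAR clause from Section 9.3.6, so that its condition is medical necessity as the investigator judges it, as in 6.4.4.
2. Make the Appendix 10.1 entry refer to both 6.4.4 and 9.3.6.
3. State in both sections that consultation must not hold up a medically necessary code break. The decide-then-notify wording that the sponsor already accepts for the UK would serve.
4. Bring the site-level unblinding instructions into line.

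The first two changes only reconcile existing text and are nearly free at the next amendment. The third is a further choice for the sponsor. Its small downside is that a few more code breaks may occur without prior discussion.
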